3. STUDY POPULATIONS

3.1 Screened Population

The screened population is defined as all screened participants, including screen failures. Screen failures will be captured and listed, including the reason for screen failure.

3.2 Safety Population

All participants receiving both investigational products will be included in the safety population.

3.3 DLT-Evaluable Population

The DLT-evaluable population is defined as all participants of Phase 1b who met all eligibility criteria, received the entire planned dose of APX005M and nivolumab during the DLT observation period and have completed a follow-up period after administration of study drug for at least 21 days (one full treatment cycle; i.e., participant does not come off study for reasons other than toxicity).

3.4 Efficacy Population

Participants evaluable for efficacy (tumor response) are defined as those who meet study eligibility criteria and have at least one on treatment (post baseline) tumor assessment.

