2.2.4 Additional exploratory efficacy analyses (Phase 2 only)

Exploratory analyses of efficacy will be carried out including occurrences of unconfirmed responses:

- ORR - including unconfirmed response (efficacy and safety population)
- DoR - including unconfirmed response (efficacy and safety population)

Exploratory analysis: Characterization of progressive disease. (efficacy population)

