2.2.6 Sensitivity efficacy analyses (Phase 2 only)

Parameters of Response by RECIST v1.1 in the safety population:

- ORR (RECIST v 1.1, safety population)
- DoR (RECIST v1.1, safety population)

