4.2 Efficacy Endpoint

- The Progression-Free Survival (PFS) is defined as the time from first dose of investigational product to the earlier of PD (by RECIST 1.1 and iRECIST) or death due to any cause. PFS will be calculated as time in months between (first date of PD or death due to any cause – date of first dose).

- For participants with no baseline assessment, PFS will be censored on the date of first dose.
- For alive participants with no post baseline tumor assessment will be censored on the date of first dose however they will be considered an event in case of record end of treatment by clinical progression within eight weeks of first treatment dose (before the first tumor assessment schedule)
- For participants who have at least 1 post baseline tumor assessment, if they do not have PD or do not die, PFS will be censored on the date of last tumor assessment documenting the absence of PD.

PFS will be summarized using the Kaplan Meier method; the median event time (if appropriate) and two-sided 90% CI for the median will be provided (Brookmeyer and Crowley method). PFS by RECIST 1.1 and by iRECIST will be summarized by dose level and overall in each tumor type for Phase 1b and by cohort for Phase 2 (including participants treated at RP2D in Phase 1b) in 2 separate tables. A graph of the Kaplan Meier curve will be presented for Phase 2 (including participants treated at RP2D in Phase 1b).

- The Best Overall Response (BOR) is defined as the best response presented according to RECIST v1.1 from the inclusion in the study to progressive disease (PD).
- The Objective Response Rate (ORR) is defined as the incidence of patients who show as best overall response a complete response (CR) or partial response (PR). The ORR can be calculated based on two tumor assessment methods, RECIST 1.1 and iRECIST.

The point estimate of the ORR will be presented along with exact two-sided 90% confidence interval (CI) using the exact method (Clopper-Pearson).

- The Duration of Response (DoR) is defined as the time in months from the first evidence of confirmed PR or better to disease progression or death due to any cause, whichever occurs earlier (by RECIST 1.1 and iRECIST). DoR will be calculated for the participants with a response of PR or better. If participants do not have PD or do not die, DoR will be censored on the date of last tumor assessment documenting the absence of PD.

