The DoR will be summarized using the Kaplan Meier method; the median event time (if appropriate) and two-sided 90% CI for the median will be provided (Brookmeyer and Crowley method). The DoR by RECIST 1.1 and iRECIST will be summarized by dose level and overall for Phase 1b and by cohort for Phase 2 (including participants treated at RP2D in Phase 1b) in 2 separate tables. A graph of the Kaplan Meier curve will be presented for Phase 2 (including participants treated at RP2D in Phase 1b).

- The 6-month Progression-Free Survival Rate (PFSR) is defined as the proportion of participants that did not have disease progression (by RECIST 1.1) or died due to any cause at 6 months from the first dose of investigational product. It will be depicted in a Kaplan Meier survival curve.

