5.4.2 Efficacy Analyses

The efficacy analysis is based on tumor assessments, which will be performed with two methods (RECIST 1.1 and iRECIST) at Screening, about every 8 weeks during Treatment Phase and Follow-up. The efficacy analysis will be performed for Efficacy Population.

ORR (and 90% confidence interval by exact distribution), DoR and PFS (Kaplan-Meier estimate) will be estimated for each cohort/group and for each tumor assessment method (by RECIST 1.1 and iRECIST).

The listings by-individual participants will be generated for the detailed tumor assessment, the response assessment by RECIST1.1 and iRECIST, and the derived DoR and PFS.

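### The SAP places PFS in a scanned-only population but also gives PFS rules for unscanned participants; following the population rule, failures before the first scan drop out of PFS and 6-month PFSR

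*SAP*

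**What the plan says.** SAP 5.4.2 states: "The efficacy analysis will be performed for Efficacy Population". Its next sentence says that "DoR and PFS (Kaplan-Meier estimate) will be estimated for each cohort/group", with no separate population for PFS. SAP 3.4 admits to that population only "those who meet study eligibility criteria and have at least one on treatment (post baseline) tumor assessment". Protocol 7.2 has the same definition. The first scan is due at 8 weeks ± 1 week.

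SAP 4.2 runs PFS from first dose to progression or death from any cause. Living participants with no post-baseline scan are censored at the date treatment began, with this exception: "however they will be considered an event in case of record end of treatment by clinical progression within eight weeks of first treatment dose". The 6-month PFSR is "the proportion of participants that did not have disease progression (by RECIST 1.1) or died due to any cause at 6 months" from first dose, shown on a Kaplan-Meier curve.

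SAP 2.2.6 plans sensitivity analyses under the heading "Parameters of Response by RECIST v1.1 in the safety population", but lists only ORR and DoR. SAP 2.2.4 adds safety-population versions of the same two endpoints with unconfirmed responses. For that set, SAP 3.2 says: "All participants receiving both investigational products will be included in the safety population". SAP 2.3.5 replaces Phase 2 participants who are not evaluable for response. Protocol 7.4.3 names no PFS population and leaves details to the SAP.

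**The concern.** A programmer cannot follow both sections. The 4.2 rules for unscanned participants act on nobody if 5.4.2 is applied, and a death before the first scan is an event under 4.2 but an exclusion under 5.4.2. Those excluded are the earliest failures, so the error has a known direction: PFS and PFSR are overstated relative to all treated participants. Replacement then fills their places with people who reached a scan.

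The planned safety-population analyses do not repair this, because none covers PFS. Moving PFS to the Safety Population would not fully repair it either. That set requires both products, nivolumab is given first (protocol 3.1), and Table 4 in protocol 3.7 stops both products after a Grade 4 nivolumab infusion reaction. Someone who received nivolumab only is in neither set, although their PFS clock has started.

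At stake is the reading of a named secondary endpoint against historical rates of 60%, 19% and 22%, for which protocol 7.1 and SAP 5.1 quote power.

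**Working it through.** **Inputs (protocol 7.1, SAP 5.1).** Cohort 1: n = 45, PFSR 60% against 80%. Cohort 2: n = 37, 19% against 38%. Cohort 3, each group: n = 37, 22% against 43%. Exponential PFS, one-sided 5%, 8 months of accrual, 6 months of follow-up.

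**The plan's own power.** Hazard λ = −ln(PFSR)/6. Expected events are n[1 − (e^(−6λ) − e^(−14λ))/(8λ)]: E0 under the null and E1 under the alternative. Power = Φ[(|ln HR| − 1.645/√E0)·√E1].

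| Cohort | HR | E0 | E1 | Power | Stated |
|---|---|---|---|---|---|
| 1 | 0.437 | 25.4 | 13.9 | 96.9% | 97% |
| 2 | 0.583 | 34.2 | 29.1 | 91.9% | 92% |
| 3 | 0.557 | 33.5 | 27.5 | 94.2% | 94% |

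The stated powers are sound. The problem is who is analysed.

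**Bias, with no test involved.** Let d be the share who die or progress clinically with no scan, among scanned participants plus such failures. The documents do not give d; I assume 2–10%. Everyone lost has failed before month 6, so only the denominator shrinks and the scanned-only PFSR is PFSR/(1 − d). If the true PFSR equals the null:

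| d | Cohort 1 | Cohort 2 | Cohort 3 |
|---|---|---|---|
| 0 | 60.0% | 19.0% | 22.0% |
| 2% | 61.2% | 19.4% | 22.4% |
| 5% | 63.2% | 20.0% | 23.2% |
| 10% | 66.7% | 21.1% | 24.4% |

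The median read from the curve is −ln[0.5(1 − d)]/λ. At d = 5% it is 8.74, 2.69 and 2.95 months, instead of 8.14, 2.50 and 2.75. The number lost while filling n is n·d/(1 − d): 45 × 0.05/0.95 = 2.4 in Cohort 1 and 37 × 0.05/0.95 = 1.9 in the others.

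**Is the range plausible?** Week 8 is 1.84 months. Under the exponential null, 1 − e^(−1.84λ) = 14.5%, 39.9% and 37.1% have an event by then. So d = 5% needs 34%, 13% and 13% of those early events to be unscanned; d = 10% needs 69%, 25% and 27%. For Cohort 1, 10% is near the ceiling.

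**Error rate, under two conditions.** This applies only if the historical rates describe all treated participants and a one-sided 5% test is run; the analysis sections plan none. From d = 0 to d = 5%, for Cohorts 1, 2 and 3:

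- Exact binomial at 6 months (reject at 33/45, 12/37, 13/37): 4.5% to 10.2%, 3.6% to 5.2%, 4.7% to 6.7%.
- Exponential-rate test with null-expected-event variance (40,000 simulated trials): 6.0% to 12.2%, 4.4% to 7.0%, 4.4% to 7.3%.

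For example, 33 of 45 event-free in Cohort 1 gives p = 0.045. Restoring two omitted failures makes it 33 of 47 and p = 0.099.

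**The case against.** The best defence is that section 4.2 is the specific PFS rule and 5.4.2 a loose general line. The label (tumor response) in SAP 3.4 suggests the set was meant for ORR, and the table shells, held in an external file that was not available, may name another population. That may well be the intent. But 5.4.2 names PFS in the next sentence, and if the shells say otherwise it is still wrong and needs correcting.

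The effect is also modest. At d = 5% the shift is 3.2, 1.0 and 1.2 points. An approximate 90% interval half-width, 1.645·√[p(1 − p)/n] at the null rates, is 12.0, 10.6 and 11.2 points. This stands, and it limits the severity. It does not make a one-directional, avoidable bias acceptable.

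No PFSR test or decision rule is planned, and the documents give no denominator for the historical rates. If those rates describe scanned participants, there is no error-rate effect. Both points stand, which is why the error rates are conditional.

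SAP 5.4.2 does not name PFSR, and 4.2 defines its failures by RECIST 1.1 progression or death. PFSR is covered as an efficacy endpoint shown on a Kaplan-Meier curve, which I take to be the PFS curve. If clinical progression were not counted for PFSR, d for that endpoint would cover deaths only.

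The nivolumab-only case is probably rare and matters only with early death or clinical progression. Living participants who stop unscanned without clinical progression are censored at first dose and do not change the curve. The loss would also be partly visible in the population counts and discontinuation reasons (SAP 5.2) and the fatal-event tables (SAP 5.4.3.3), but no planned estimate corrects it.

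**Conclusion.** The contradiction is real and nothing in the two documents resolves it. Following 5.4.2 as written biases PFS and 6-month PFSR upward relative to all treated participants whenever someone dies or progresses clinically before a scan. At an assumed 5% lost, PFSR reads about 3 points high in Cohort 1 and about 1 point high in Cohorts 2 and 3. At 10% the excess is 6.7, 2.1 and 2.4 points. If the historical rates describe all treated participants and a 5% test were applied, 5% lost would raise the type I error by about 6 points in Cohort 1 and by 1.5 to 3 points in Cohorts 2 and 3 under the two tests shown. All of this rests on the assumed share lost and, for the medians and error rates, mostly on the plan's exponential null. PFSR is secondary and ORR drives go/no-go, so this should be fixed before analysis but does not undermine the primary conclusion.

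**What to change.** In SAP 5.4.2, state that Phase 2 PFS and 6-month PFSR are analysed in all participants who received any dose of APX005M or nivolumab, that those without a post-baseline assessment follow section 4.2, and that the Efficacy Population analysis is supportive. Align the external table shells. Do not define the set by enrolment, because protocol 3.1 ties it to receipt of any product and protocol 5.2.1 to signing consent. If the Safety Population is used instead, list anyone who received nivolumab only.

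Leave the Simon decision in response-evaluable participants. Three smaller items:

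- Beside the Simon result, show the already planned safety-population ORR with unscanned participants as non-responders, and the number replaced by reason.
- SAP 5.3 removes every major deviation from the efficacy set, whereas SAP 3.4 and protocol 7.2 exclude only eligibility violations and unscanned participants. Confine the removal of other major deviations to a supportive analysis.
- State which denominator the historical PFSR rates use.

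The cost is SAP wording, shell alignment and one extra PFS/PFSR analysis. No protocol change is needed, and the inputs are already collected: reason for stopping treatment (protocol 4.1) and death (protocol 6.3.2). Reported PFS and PFSR may come out slightly lower.

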4. DEFINITION OF STUDY ENDPOINTS AND DERIVED VARIABLES

4.1 Baseline and Demographics Characteristics

Demographics and baseline characteristics by cohort/group will be summarized using descriptive statistics.

- Time from diagnosis is defined as the time elapsed (in months) since the date of first positive biopsy for this disease until the informed consent date.

4.2 Efficacy Endpoint

- The Progression-Free Survival (PFS) is defined as the time from first dose of investigational product to the earlier of PD (by RECIST 1.1 and iRECIST) or death due to any cause. PFS will be calculated as time in months between (first date of PD or death due to any cause – date of first dose).

- For participants with no baseline assessment, PFS will be censored on the date of first dose.
- For alive participants with no post baseline tumor assessment will be censored on the date of first dose however they will be considered an event in case of record end of treatment by clinical progression within eight weeks of first treatment dose (before the first tumor assessment schedule)
- For participants who have at least 1 post baseline tumor assessment, if they do not have PD or do not die, PFS will be censored on the date of last tumor assessment documenting the absence of PD.

PFS will be summarized using the Kaplan Meier method; the median event time (if appropriate) and two-sided 90% CI for the median will be provided (Brookmeyer and Crowley method). PFS by RECIST 1.1 and by iRECIST will be summarized by dose level and overall in each tumor type for Phase 1b and by cohort for Phase 2 (including participants treated at RP2D in Phase 1b) in 2 separate tables. A graph of the Kaplan Meier curve will be presented for Phase 2 (including participants treated at RP2D in Phase 1b).

- The Best Overall Response (BOR) is defined as the best response presented according to RECIST v1.1 from the inclusion in the study to progressive disease (PD).
- The Objective Response Rate (ORR) is defined as the incidence of patients who show as best overall response a complete response (CR) or partial response (PR). The ORR can be calculated based on two tumor assessment methods, RECIST 1.1 and iRECIST.

The point estimate of the ORR will be presented along with exact two-sided 90% confidence interval (CI) using the exact method (Clopper-Pearson).

- The Duration of Response (DoR) is defined as the time in months from the first evidence of confirmed PR or better to disease progression or death due to any cause, whichever occurs earlier (by RECIST 1.1 and iRECIST). DoR will be calculated for the participants with a response of PR or better. If participants do not have PD or do not die, DoR will be censored on the date of last tumor assessment documenting the absence of PD.

The DoR will be summarized using the Kaplan Meier method; the median event time (if appropriate) and two-sided 90% CI for the median will be provided (Brookmeyer and Crowley method). The DoR by RECIST 1.1 and iRECIST will be summarized by dose level and overall for Phase 1b and by cohort for Phase 2 (including participants treated at RP2D in Phase 1b) in 2 separate tables. A graph of the Kaplan Meier curve will be presented for Phase 2 (including participants treated at RP2D in Phase 1b).

- The 6-month Progression-Free Survival Rate (PFSR) is defined as the proportion of participants that did not have disease progression (by RECIST 1.1) or died due to any cause at 6 months from the first dose of investigational product. It will be depicted in a Kaplan Meier survival curve.

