5.5 Efficacy Assessments

Tumor assessment will be performed within 21 days prior to start of investigational products and during Treatment Phase every 8 ± 1 weeks. Complete or partial responses should be confirmed at a subsequent time point 4-5 weeks later.

Tumor assessments for the purpose of establishing the Phase 2 primary endpoint will follow RECIST 1.1 guidelines.

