7.1 Sample Size Determination

This is a Phase 1b-2, study. The sample size for the Phase 1b dose-escalation cannot be precisely estimated but depends upon the observed toxicities. Cohorts of 3 to 6 subjects will be treated at each DL during dose escalation portion of the study. It is anticipated that approximately 18 subjects will be treated in this portion of the study depending on the actual rate of DLTs.

Sample size for Phase 2 is calculated using the Simon optimal 2-stage design [32]:

- **Cohort 1 (inNSCLC):** Assuming a false positive rate (α) of 0.1 (one-sided), a false negative rate (β) of 0.1, a response probability of poor drug (P0) of 22% and a response probability of good drug (P1) of 40%, first stage sample size (n1) is 24 and the maximum sample size (n) is 45 response evaluable subjects. In the first stage, if there are 5 or less responses in 24 subjects, the enrollment in this cohort will be stopped. Otherwise, if 6 or more responses are observed, 21 additional subjects will be accrued in Stage 2 for total of 45. Enrollment may continue into Stage 2 while the planned number of subjects for Stage 1 are followed for efficacy. By the end of Stage 2, if 13 or less responses are observed in 45 subjects, then no further investigation is warranted. If 14 or more responses are observed, the null hypothesis will be rejected and true RR is 40%.

The sample size of 45 subjects, provides 97% power to statistically test the null hypothesis of historical 6-month PFS rate (PFSR) of 60% (estimated for pembrolizumab in Keynote-024 [33]) versus the alternative hypothesis of 6-month PFSR rate of 80%. This calculation assumes exponential PFS, 1-sided 5% type I error rate, enrollment of subjects for 8 months with 6 months of follow-up prior to conducting the final analysis.

- Cohort 2 (PD1-MM): Assuming α of 0.1 (one-sided), β of 0.1, P0 5% and P1 of 20%, n1 is 12 and n is 37 response evaluable subjects. In the first stage, if there are no responses in 12 subjects, the enrollment in this cohort will be stopped. Otherwise, if 1 or more responses are observed, 25 additional subjects will be accrued in Stage 2 for total of 37. Enrollment may continue into Stage 2 while the planned number of subjects for Stage 1 are followed for efficacy. By the end of Stage 2, if 3 or less responses are observed in 37 subjects, then no further investigation is warranted. If 4 or more responses are observed, the null hypothesis will be rejected and true RR is 20%.

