5.4 Summary of Statistical Methods

Participants treated at the RP2D in Phase 1b will be included in Stage 1 of the relevant disease-specific cohort for Phase 2. All the data (e.g., safety and efficacy) from these participants will be used in the relevant summary tables and listings for both Phase 1b and Phase 2 (including participants treated at RP2D in Phase 1b).

All relevant participant data will be included in listings. All participants entered into the database will be included in participant data listings. The listings will be generally sorted by first dose level (Phase 1b) or

cohort (Phase 2, including participants treated at RP2D in Phase 1b) and then Participant ID, unless specified otherwise.

All applicable data will be summarized by dose level and overall for Phase 1b, and by cohort and overall for Phase 2 (including participants treated at RP2D in Phase 1b), unless specified otherwise. In addition, data will be summarized by visit and/or time-point when appropriate. Unscheduled or repeat assessments will not be included in summary tables but will be included in listings.

Continuous variables will be summarized using the number of observations (n), mean, standard deviation (SD), median, Q1, Q3, minimum, and maximum along with the total number of patients contributing values.

Descriptive statistics for categorical/qualitative data will include frequency counts and percentages. The total number of participants in the dose level or cohort (N) will be used as the denominator for percent calculations, unless stated otherwise in the table footnote.

Kaplan-Meier model will be used to analyze duration of response, PFS and OS. In all these analyses, in addition to the Kaplan-Meier curve, median, Q1, Q3 and their corresponding CI 95%, number of events and censored cases distribution will be shown.

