7. TABLES, LISTINGS AND FIGURES

This information has been detailed and collected in an external document with the following file name:
APX002 - Statistical Analysis Plan TFLs v2.0 -04FEB2021.docx

Note: The final report of phase 1b was performed based on the SAP and TFLs version 1.0 (30MAY2016)

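### The SAP sets both 90% and 95% confidence levels for median PFS and DoR, and rejecting H0 is reported as proving the target response rate

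*SAP*

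**What the plan says.** **Confidence level.** SAP 4.2 treats the two time-to-event endpoints alike. For progression-free survival: "PFS will be summarized using the Kaplan Meier method; the median event time (if appropriate) and two-sided 90% CI". For duration of response: "The DoR will be summarized using the Kaplan Meier method; the median event time (if appropriate) and two-sided 90% CI". Both name the Brookmeyer–Crowley method.

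SAP 5.4 has a general paragraph on Kaplan–Meier output: "Kaplan-Meier model will be used to analyze duration of response, PFS and OS". It then requires, for all of these analyses, "median, Q1, Q3 and their corresponding CI 95%, number of events and censored cases distribution will be shown". The first and third quartiles get intervals only here.

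Protocol 7.4.3 and SAP 5.4.2 give 90% for the ORR interval and no level for PFS or DoR. SAP section 7 refers the table shells elsewhere: "This information has been detailed and collected in an external document with the following file name".

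**Conclusion after rejection.** Protocol 7.1 says for Cohort 1: "If 14 or more responses are observed, the null hypothesis will be rejected and true RR is 40"%. For Cohort 2, and for each group of Cohort 3: "If 4 or more responses are observed, the null hypothesis will be rejected and true RR is 20"%. SAP 5.1 repeats both conclusions.

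**The concern.** SAP 4.2 and 5.4 prescribe different levels for one statistic, so two programmers working from one SAP would produce different tables. The reported limits of secondary (RECIST 1.1) and exploratory (iRECIST) medians would then depend on which section was followed. In an open-label study that choice could be made after the data are seen.

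The second point is one of inference. A Simon test that rejects H0 shows that the response rate exceeds P0. P1 is only the rate at which power was set. A report that copied the sentence would claim a rate for the primary endpoint that the test does not establish.

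**Working it through.** **1. Is the conflict real?**

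| | SAP 4.2 | SAP 5.4 |
|---|---|---|
| Endpoints | PFS, DoR | DoR, PFS, OS |
| Median | 90% CI | 95% CI |
| Quartiles | not mentioned | 95% CI |
| Method | Brookmeyer–Crowley | not stated |

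Both sections cover median PFS and median DoR. The exceptions clauses in SAP 5.4 for cases specified elsewhere concern sorting, grouping and denominators, not the Kaplan–Meier sentence. OS is not an objective or endpoint in either document, so the 5.4 sentence looks less specific to this trial than 4.2.

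**2. How much can the limits move?** The normal quantiles are 1.960 (95%) and 1.645 (90%), and 1.960 / 1.645 = 1.19. A 95% interval is therefore about 19% wider on the standard-error scale.

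The effect on a Kaplan–Meier median depends on the scan dates, so it was simulated (3,000 trials per scenario, 2,000 for shift sizes).

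- Inputs from Protocol 7.1: 6-month PFS rates of 19%, 38%, 22% and 43% with n = 37, and 60% and 80% with n = 45; exponential PFS; 8 months of enrolment plus 6 months of follow-up.
- Scan schedule from Protocol 5.5: "during Treatment Phase every 8 ± 1 weeks". It was run exactly every 8 weeks and with uniform ±1 week variation.
- Censoring at the last scan, as in SAP 4.2. Progression is dated to the first scan at or after it.
- Assumptions not in the documents: log-log transform for the limits, no dropout, no deaths between scans.

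| | Exact 8 weeks | ±1 week |
|---|---|---|
| Trials where 90% and 95% limits differ at one or both ends | 23–39% | 87–92% (38% in Cohort 1 at 80%) |
| Size when they differ | typically one scan interval: 56 days = 1.84 months | median 0.03–0.4 months; 90th percentile 1.4–2.0 months |
| Cohort 1 at 60%: upper limit not reached, 90% vs 95% | 55% vs 67% | 37% vs 50% |

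DoR was not simulated.

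**3. Does rejection establish P1?** The exact rejection probability is

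P(reject | p) = Σ over x > r1 of P(X1 = x) · P(X2 > r − x), with X1 ~ Bin(n1, p) and X2 ~ Bin(n − n1, p).

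Cohort 1 has n1 = 24, r1 = 5, n = 45, r = 13. Cohorts 2, 3A and 3B have n1 = 12, r1 = 0, n = 37, r = 3.

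The plan's own figures come first. Cohort 1 gives alpha 0.0937 at 22% and power 0.900 at 40%. The other cohorts give alpha 0.0935 at 5% and power 0.902 at 20%. All meet the stated 0.1 limits. A full search returns the same boundaries as the Simon optimal designs.

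At rates between P0 and P1:

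| Cohort 1, true rate | P(reject) | Cohorts 2 and 3, true rate | P(reject) |
|---|---|---|---|
| 25% | 0.203 | 8% | 0.294 |
| 30% | 0.468 | 10% | 0.447 |
| 35% | 0.732 | 15% | 0.751 |

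The smallest rejecting counts are 14/45 = 31.1% and 4/37 = 10.8%, both well below P1. Their exact 90% intervals are 19.9–44.3% and 3.8–23.1%, so neither singles out 40% or 20%.

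**The case against.** **The level may already be settled.** The shells are in a separate file that was not available for this review, and they may fix it. SAP 4.2 is also the more specific text, so the likely intent can be inferred. Both points are fair, but the SAP itself still gives two instructions and no order of precedence.

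**The consequences are small.** The primary endpoint is ORR, whose interval is 90% throughout. The decision rules are stated in full as counts, and no planned output is labelled a true response rate. This stands, and it makes both points matters of reporting. The rejection probabilities above would be similar in kind for any Simon design; they show why the sentence is wrong, not that the design is.

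**The simulation overstates the difference.** Intervals at two levels are expected to differ, and with varying scan dates many differences are of the order of a day. That is correct: the 87–92% figure should be read with the median shift beside it. The finding rests on the text.

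**The quartiles are not in conflict.** Only SAP 5.4 gives them intervals. This is true; using one level for the median and quartiles in the same table is ordinary consistency.

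**Conclusion.** Both points hold. The SAP sets two confidence levels for median PFS and median DoR without saying which applies. This certainly affects what is reported. Its numerical size depends on scan timing and on the assumptions listed above, from about a day to a whole scan interval or more, and it can decide whether an upper limit is reported at all.

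The stated conclusion after rejection is wrong as written in both documents and for every Phase 2 cohort. This part needs no assumption beyond binomial response counts. It is a wording error: the thresholds, sample sizes, alpha (0.094 in each design) and power (0.90) are sound. Both points should be corrected, and neither affects a go/no-go decision.

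**What to change.** 1. Before the analysis, state one level in SAP 4.2 and 5.4. The choice is the sponsor's, but 90% fits the endpoint text and the ORR interval. That means changing 95% to 90% in SAP 5.4 for the median and both quartiles.
2. Remove OS from the SAP 5.4 sentence, or define it as an endpoint.
3. Check the external table shells against the chosen level.
4. In SAP 5.1 and Protocol 7.1, replace the statement about the true rate with: H0: RR ≤ 22% is rejected (Cohort 1); H0: RR ≤ 5% is rejected (Cohorts 2, 3A and 3B).

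The SAP edits cost almost nothing. A change to Protocol 7.1 brings the ethics-committee steps in Protocol 8.1.1 and 8.1.2. If an amendment is not convenient, correcting the SAP alone is enough to keep the error out of the report. Design, sample size, boundaries and data collection do not change.
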